#### 14.3. Reporting of adverse events

##### 14.3.1. Reporting of (S)AEs and device deficiencies by the investigator to the sponsor

Adverse events will be reported between the first use of the medical device and the last study related activity. Medical events that occur between signing of the Informed Consent and the first use of the medical device will be documented as medical history data.

All (S)AEs will be recorded in the patient's file and in the eCRF.

**All SAEs and device deficiencies will be reported immediately but no later than 3 calendar days after investigational site study personnel's awareness of the event to:**

- Sponsor: [name]. E-mail: [[contact]](mailto:[contact])
- Health Innovation and Research Institute:  
E-mail: [[contact]](mailto:[contact])

[contact]

[contact]

Address: [name]

This reporting is done by using the appropriate SAE form and device deficiency form. Follow-up information should be provided as necessary

#### 14.4. Annual Safety and progress Reporting

Sponsor will inform all principal investigators at least annually in writing of all the serious adverse events at all investigation sites that have been reported to the sponsor, and ensure that they are reported to their local EC, if defined by their institution's procedure.

### 15 Notification of end of clinical investigation, early termination and temporary halt

Early termination or temporary halt of the clinical investigation or an investigational site may be necessary in case of major non-compliance, critical safety issues or premature study discontinuation. This can occur at any time by the sponsor, principal investigator of the local site, IEC. ISO 14155:2011 shall be followed.

Alle deelnemers zullen hiervan persoonlijk of via hun individueel begeleider (IB) op de hoogte worden gesteld.

In case of an early termination, all study materials will be retained and the terminating party shall justify its decision in writing.

## Study Analysis

### 16.1 Sample Size Calculation

The primary endpoint selected was a change in the VAS score for relaxation, where an average improvement of 0.5 out of 10 is considered clinically relevant.

The standard deviations used (0.83 for standard relaxation and 0.74 for VRelax) were estimated based on the results of a comparable study in an outpatient setting, as described in the article by Veling et al. (2021).

The chosen statistical power was 80%, and the type I error rate (alpha) was set at 0.05.

Calculations were performed using the software program **GPower**.

To determine the required sample size using the VAS relaxation score as the primary outcome measure:

- With an expected dropout rate of 30%, the final **sample size = 54**.

---

### 16.2 Statistical Analysis

Randomisation of participants into the two groups will be performed using SAS software.

The relaxing effect will be calculated by comparing the changes in VAS scores before and after each session. This is calculated as:

**1 - (VAS score before / VAS score after)**

Descriptive statistics (mean, standard deviation, minimum, and maximum) will be computed for demographic, clinical, and outcome variables.

VAS scores for relaxation and happiness, as well as physiological parameters (heart rate, HRV, skin conductance, respiration), will be compared using **paired t-tests** between pre- and post-session time points.

Perceived Stress Scale (PSS) scores will also be compared between pre- and post-therapy blocks (each block consisting of 10 sessions) using a paired t-test.

To estimate the difference in effect between the VR treatment and standard relaxation, a **mixed model multilevel regression analysis** will be used. The model will include:

- Time (before vs after)
- Treatment (VR vs standard)
- Group (1 vs 2)
- Interaction term: Time × Treatment  
(with random intercept for “participant”)

The **interaction between time and treatment** is the primary parameter of interest.

Finally, **carry-over effects** will be examined by comparing VAS scores and physiological parameters between session 1, session 5, and session 10 using paired t-tests (S1 vs S5 and S5 vs S10).

---

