## Hypothesis of the Clinical Investigation

1. VRelax will reduce acute stress: the PRE-VAS score will be higher than the POST-VAS score.
2. VR relaxation will have a greater relaxing effect than standard relaxation: VAS scores and biomarkers will reflect a stronger relaxation effect.
3. VRelax will also reduce chronic stress through a cumulative effect, meaning the post-intervention PSS score will be lower than the pre-intervention PSS score.
4. There will be a difference in the acute effect over time; in other words, as the number of sessions increases, habituation or boredom may occur for both standard and VR relaxation. This will be measured by a decreasing difference between pre- and post-VAS scores per individual over time.

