## **7. Objective of the Clinical Investigation**

### **7.1 Primary Objectives**

The main objective is to examine the relaxing effect of VRelax. We aim to measure the magnitude and duration of the effect and assess the difference compared to standard relaxation exercises. What is the immediate effect, and what is the long-term impact? Is there any habituation? Which physiological parameters are most influenced?

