## **8. Endpoints**

### **8.1 Primary Endpoint**

The primary endpoint is the VAS score for relaxation. We will examine whether there is a change in the relaxation VAS score between the time points before and after a relaxation session, with an average improvement of 0.5 out of 10 considered clinically relevant.

The main goal is to determine whether VR relaxation is an effective method for our population.

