## **10. Population**

### **10.1 Number of Subjects**

The primary endpoint selected is a change in the VAS relaxation score, where an average improvement of 0.5 out of 10 is considered clinically relevant between pre- and post-session time points.

The standard deviations used (0.83 for standard relaxation and 0.74 for VRelax) were estimated based on the results of a comparable study in an outpatient population, as described in the article by Veling et al. (2021).

The chosen statistical power is 80%, and the type I error rate was set at 0.05.

An expected dropout rate of 30% was included.

Calculations were performed using the GPower software.

The calculated required sample size for detecting a difference in VAS relaxation scores is **54**.

All participants are forensic psychiatric patients admitted to PC Sint-Jan Baptist in Zelzate and expected to remain there for at least 4 more months, ensuring their availability throughout the entire study period.

---

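### Section 16.2 defines the per-session relaxing effect as a before/after ratio that no endpoint, test or model names and that has no fixed equivalent of the 0.5-point threshold

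*Combined protocol and SAP*

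**What the plan says.** Section 16.2 introduces its effect measure with this sentence: "The relaxing effect will be calculated by comparing the changes in VAS scores before and after each session". The formula directly below it is "1 - (VAS score before / VAS score after", followed by the closing bracket. It is the only effect formula in the section, and nothing marks it as exploratory or supplementary. The next sentence reads: "Descriptive statistics (mean, standard deviation, minimum, and maximum) will be computed for demographic, clinical, and outcome variables".

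Section 7.1 gives the same term a central place: "The main objective is to examine the relaxing effect of VRelax. We aim to measure the magnitude and duration of the effect".

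The rest of the plan works in VAS points:

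- Section 8.1 takes the before-to-after change in the relaxation VAS as the primary endpoint, "with an average improvement of 0.5 out of 10 considered clinically relevant".
- Section 10.1 repeats this for the sample size: "an average improvement of 0.5 out of 10 is considered clinically relevant between pre- and post-session time points".
- Section 16.1 says "The primary endpoint selected was a change in the VAS score for relaxation", with the same 0.5 threshold and SDs of 0.83 and 0.74.
- Hypothesis 4, on habituation, also uses a difference: "This will be measured by a decreasing difference between pre- and post-VAS scores per individual over time".
- After the formula, section 16.2 compares VAS scores before and after sessions by paired t-test. It then fits a mixed model with time, treatment, group and a time-by-treatment interaction, and compares VAS scores between sessions 1, 5 and 10. The ratio is not mentioned again, and no threshold is given on its scale.

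**The concern.** The trial's relevance question is whether the mean improvement reaches half a point. The only formula the plan gives for the size of the effect is unitless and has the post-session score as its denominator. An analyst who follows section 16.2 literally would produce a per-session effect, and a mean, SD, minimum and maximum of it, that cannot be set against 0.5 without knowing each score behind it. The plan would also hold two definitions of effect size, one in points and one a ratio, with no statement of which governs. That leaves a choice of scale that could be made after the data are seen.

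**Working it through.** **Inputs.** The formula is from section 16.2 and the 0.5 threshold from sections 8.1, 10.1 and 16.1. SDs 0.83 and 0.74, 80% power, alpha 0.05, 30% dropout and N = 54 are from section 16.1. The example scores are illustrative, because the documents give no VAS means or distributions.

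**Step 1: on which scale was N = 54 computed?** A paired t-test on the point scale can reproduce it. With difference 0.5 and within-person correlation assumed to be 0 (none is stated), the SD of the difference is √(0.83² + 0.74²) = √1.2365 = 1.112. Two-sided alpha 0.05 and 80% power give n = 41, and 41 × 1.3 = 53.3, rounded up to 54. Dividing by 0.7 instead gives 59. With an assumed correlation of 0.1, n = 37 and 37 / 0.7 = 52.9, or 53. The route is not stated, so this is not proof. It does show that N can be obtained in points without the ratio.

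**Step 2: rewrite the formula.** With b = before and a = after, 1 − b/a = (a − b)/a. The ratio is the point change divided by the post-session score.

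**Step 3: put the threshold on the ratio scale.** A gain of 0.5 from b gives 0.5/(b + 0.5).

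| Before | After | Point change | Ratio |
|---|---|---|---|
| 1 | 1.5 | +0.5 | +0.333 |
| 3 | 3.5 | +0.5 | +0.143 |
| 5 | 5.5 | +0.5 | +0.091 |
| 9 | 9.5 | +0.5 | +0.053 |

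The largest value is about six times the smallest (0.333 / 0.053 = 6.3). No single ratio value corresponds to 0.5 points.

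**Step 4: denominator and asymmetry.** At a = 0 the ratio is undefined, and the plan has no rule for that case. Going from 4 to 5 gives 1 − 4/5 = +0.20, while 5 to 4 gives 1 − 5/4 = −0.25. Gains cannot exceed 1; losses have no lower limit.

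**Step 5: averages.** For one session with a positive post score, the ratio has the same sign as the point change. An average need not, because each change is weighted by 1/a.

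| Two sessions | Mean point change | Ratios | Mean ratio |
|---|---|---|---|
| 3→2.5, 7→7.8 | +0.15 | −0.200, +0.103 | −0.049 |
| 3→3.6, 7→7 | +0.30 | +0.167, 0 | +0.083 |
| 3→3, 7→7.8 | +0.40 | 0, +0.103 | +0.051 |

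The first row reverses the sign. The second and third reverse the ranking: the set with the larger mean gain in points has the smaller mean ratio.

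**Step 6: is there a fixed direction of bias when nothing changes on average?** No. For 3→4 with 7→6 the mean change is 0 and the mean ratio is (0.250 − 0.167)/2 = +0.042. For 4→3 with 6→7 the mean change is again 0, but the mean ratio is (−0.333 + 0.143)/2 = −0.095. In the first pair scores are closer together after the session, and in the second further apart. The direction depends on the pre- and post-session spread, which the documents do not give.

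**Step 7: can the specified analyses use the ratio?** The paired t-tests are described as comparing VAS scores. A model with a before/after time factor needs a score at each time point, and the ratio gives one value per session, so it cannot be that model's outcome.

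**The case against.** The strongest reply is that nothing of consequence depends on the formula. The paired t-tests, the mixed model and the descriptive summaries of outcome variables in section 16.2 all yield estimates in points that can be read against 0.5. The ratio is then a surplus definition, and no point-scale estimate is lost. That stands, and it limits the point to the stated effect measure. It does not remove it, because section 16.2 attaches the formula to the term that section 7.1 uses for the main objective.

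The ratio might also be defended as an ordinary relative change. It divides by the post score rather than by baseline, has no rule for zero, and is not labelled descriptive, so that defence fails as the text is written.

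A reader might infer three stronger things that the documents do not support:

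- **That the confirmatory results or N = 54 are invalid.** The tests and model appear to use VAS scores, and N can be reproduced in points.
- **That the mean ratio is generally below zero when there is no mean change.** Step 6 shows that it can fall on either side.
- **That benefit will show as a negative effect.** This holds only if the VAS is scored as stress. Sections 8.1, 10.1, 16.1 and 16.2 name a relaxation VAS, on which a single-session gain is positive. Hypothesis 1, which expects the score to fall, and section 13.1, which lists stress/tension, point the other way. That naming conflict exists whatever formula is used.

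**Conclusion.** The point holds, with limited reach. Section 16.2 defines the relaxing effect on a scale that conflicts with the endpoint, the threshold and the sample size, and that no endpoint, test or model names. A 0.5-point gain maps to anything from +0.053 to +0.333 for starting scores between 9 and 1, and averaged ratios can reverse a ranking or a sign. These results are algebra and need no assumption about the data, except that the undefined case matters only if a post score of 0 can be recorded. How often reversals would occur, and which way the average would lean, cannot be sized from the documents.

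The specified tests, the time-by-treatment model, the hypothesis 4 measure and N = 54 appear unaffected. For the mixed model this rests on its time factor, since its outcome is not named outright. The formula should be corrected before analysis; it does not threaten the confirmatory results.

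**What to change.** - In section 16.2, replace the formula with post minus pre in VAS points, signed so that positive means benefit. Report the mean with a confidence interval against 0.5.
- If a relative change is kept, label it descriptive only and give a rule for zero scores.
- State that the mixed model's outcome is the VAS score at each time point.
- Separately, reconcile hypothesis 1 and sections 8.1, 13.1 and 16.2 so that they name the same primary VAS and its direction. On a stress/tension VAS, every improvement with a positive post score would make the present formula negative (5 to 4.5 gives 1 − 5/4.5 = −0.111).

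The cost is wording. The sample size and the specified tests do not change, and no new data are needed if the scale named is the one on the paper form.

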### Sub-hypotheses:

1. The difference in effect between standard and VR relaxation will be greater in patients with intellectual disabilities, as they have a less developed capacity for imagination.

2. There are differences in video preferences among patients with different psychiatric disorders. For example, individuals with autism may prefer static videos, while those with borderline personality disorder may prefer interactive videos.
3. The relaxing effect will manifest more quickly when using VR than with standard relaxation.

---

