### **8.2 Secondary Endpoints**

The secondary endpoint is the VAS score for happiness. We will assess whether there is a change in the VAS happiness score before and after a relaxation session, with a clinically relevant threshold of 0.5 out of 10.

Additionally, physiological parameters measured using the Embrace Plus device are also considered important secondary endpoints.

---

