## **13. Methodology**

### **13.1 Study-Specific Procedures**

The study consists of two blocks of 10 sessions: one block with VR and one without. Each participant thus serves as their own control.

The control sessions take place in the VR room, seated, with a total duration of 30 minutes (including 20 minutes of relaxation of their choice, e.g., reading, listening to music, watching a short film, body scan, etc.). The selected relaxation method is recorded for each session.

The VR sessions also take place in the VR room, seated, with a duration of 30 minutes (including 20 minutes of VRRelax with one or more 360° videos of the participant's choice). Guided meditation sessions are excluded, as they require the eyes to be closed. The selected videos are recorded per session.

Before and after each session, stress is assessed using VAS scores for stress/tension and happiness. At the beginning and end of each 10-session block, general stress levels are measured using the Perceived Stress Scale (PSS). After the final session of each block, a structured qualitative interview is conducted regarding the user experience. All groups receive the same pre- and post-intervention assessments.

During each relaxation session, physiological parameters are also measured using the Embrace Plus device ([www.Empatica.com](http://www.Empatica.com)), including heart rate, heart rate variability (HRV), respiratory rate, skin conductance, and skin temperature.

---

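### No planned analysis can test whether relaxation sets in faster with VR: physiology recorded during the session is analysed only as before and after values, with no windows defined

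*Combined protocol and SAP*

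**What the plan says.** Section 13.1 gives the two kinds of outcome different timing. For self-report: "Before and after each session, stress is assessed using VAS scores for stress/tension and happiness". For physiology: "During each relaxation session, physiological parameters are also measured using the Embrace Plus device". It lists five signals: heart rate, heart rate variability, respiratory rate, skin conductance and skin temperature. Control sessions are described "with a total duration of 30 minutes (including 20 minutes of relaxation of their choice", and VR sessions "with a duration of 30 minutes (including 20 minutes of VRRelax with one or more 360° videos".

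Section 8.2 says that "physiological parameters measured using the Embrace Plus device are also considered important secondary endpoints".

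Section 16.2 names "physiological parameters (heart rate, HRV, skin conductance, respiration" and compares them, with the VAS scores, by paired t-test "between pre- and post-session time points". The VR versus standard comparison is a mixed model with Time (two levels), Treatment, Group, a Time by Treatment interaction and a random intercept per participant. Physiology also enters paired t-tests of session 1 against 5 and session 5 against 10.

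The third sub-hypothesis reads: "The relaxing effect will manifest more quickly when using VR than with standard relaxation".

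**The concern.** A claim about speed of onset needs measurements at several times within a session. The plan collects such a record and then reduces it to one value at each end, which cannot separate an early effect from a late one.

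The reduction itself is also unspecified. A continuous signal becomes a pre and a post value only once the timing, length and summary measure are fixed, and heart rate variability in particular has to be computed over some interval. Sections 13.1 and 16.2 give none of these, so two analysts following the plan could report different results. Section 24.2 limits access to the raw Embrace Plus data to the investigator, and no section describes deriving these values blind to treatment. Windows chosen later could therefore be chosen with treatment known.

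At stake are a stated hypothesis that would go unanswered although suitable data will exist, and the reproducibility of secondary endpoints that the protocol itself calls important. Hypothesis 2 also relies on the biomarkers, alongside VAS, to show a stronger effect of VR.

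**Working it through.** The plan gives no figure for the physiological endpoints. Its one sample size, 54, was set for VAS relaxation. It reproduces with a two-sided paired t-test, difference 0.5, SDs 0.83 and 0.74, 80% power and an assumed correlation of 0: n = 41, and 41 × 1.3 = 53.3, rounded up to 54. Nothing below changes it. The check is therefore mainly a comparison of sections.

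**1. Can any planned analysis see onset within a session?**

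| Planned element | Times within a session | Can it show speed of onset? |
|---|---|---|
| VAS (13.1) | 2: before, after | No |
| Paired t-tests on physiology (16.2) | 2: pre, post | No |
| Mixed model (16.2) | 2 levels of Time | No |
| Sessions 1, 5 and 10 (16.2) | Compares sessions with each other | No |
| Embrace Plus recording (13.1) | Throughout the session | Yes, but no time-course analysis is planned |

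**2. Is there room for pre and post windows?** Time outside relaxation = 30 − 20 = 10 minutes per session, in both conditions. The documents assign it to nothing. A window of w minutes at each end needs 2w ≤ 10, less any set-up time. Two 5-minute windows would use all of it (2 × 5 = 10), so w would have to be shorter if set-up or VAS falls inside the 30 minutes.

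**3. Are all recorded parameters analysed?** Five are recorded (13.1) and four are listed for analysis (16.2). Skin temperature is missing.

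**4. What would an onset analysis look like?** With 5-minute bins there are 20 / 5 = 4 bins per session. Over 20 sessions that gives 4 × 20 = 80 values per parameter per participant. These are correlated within session and over time, so the participant intercept in 16.2 is not enough.

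Let D(b) be the VR minus standard difference in change from the pre window to bin b, signed so that positive means more relaxed with VR. A usable onset contrast is C = D(1) − D(4). Because the pre value is subtracted from both bins, it cancels, and C is the bin (first versus last) by treatment interaction. If VR reaches the same final effect sooner, D(1) > 0 and D(4) = 0, so C > 0.

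There is one limit. Suppose both conditions reach the same fraction f of their final effects, A(VR) and A(std), in the first bin. Then C = f[A(VR) − A(std)] − [A(VR) − A(std)] = −(1 − f)[A(VR) − A(std)]. With equal speed, C is below zero if VR has the larger final effect and above zero if it has the smaller one. D(1) and D(4) must therefore be reported beside C.

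**The case against.** The strongest reply is that little is broken. Physiology measured during a 30-minute session with 20 minutes of relaxation can supply before and after values from its two ends, so the paired t-tests can be run, and unspecified windows taken alone are missing detail. Speed of onset is a sub-hypothesis: it is not an endpoint in section 8, and section 7 names magnitude, duration and habituation but not onset. The primary result does not depend on it. A binned analysis also brings serial correlation and more tests.

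Most of this stands and limits the point. It does not supply an analysis for sub-hypothesis 3, and the added correlation and testing can be handled by the model and a single named contrast.

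Three stronger readings are tempting, and the documents do not support them:

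- A reader might infer that the pre and post comparison has no recording behind it. The 10 minutes outside relaxation could provide one. The plan neither says so nor rules it out.
- A reader might multiply out 54 × 20 sessions × 20 minutes = 21,600 minutes = 360 hours and call that unanalysed. The figure ignores the planned 30% dropout (if dropouts contributed nothing, 0.7 × 360 = 252 hours). In-session data may also enter the descriptive statistics and the comparison of sessions 1, 5 and 10. Only the within-session time course is certainly unused.
- A reader might infer that putting the headset on and off disturbs the VR recordings but not the control ones. No section says when recording starts or stops relative to the headset, that fitting it affects the signals, or what set-up the control activities need.

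**Conclusion.** The point holds in this form: sub-hypothesis 3 has no analysis that can test it, although the recording already planned could do so. The before and after comparison of physiology has no defined windows, and one of five recorded parameters is missing from the analysis list.

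It is a worthwhile improvement rather than a threat to the trial. No numerical bias can be attached to it, and neither the VAS relaxation endpoint nor the sample size is affected. The conclusion assumes that the Embrace Plus records through the relaxation period, as 13.1 indicates, and that the roughly 10 remaining minutes are at least partly free for short seated recordings. The documents do not confirm the second assumption, so it should be checked against the session routine.

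**What to change.** **Existing comparison (13.1 and 16.2).** Keep it. Define a seated pre window and a post window within the roughly 10 minutes outside relaxation, identical for VR and standard sessions. State their timing, length and the summary measure for each parameter. Add skin temperature to the list in 16.2.

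**Sub-hypothesis 3 (16.2).** Add a mixed model of the 20 minutes of relaxation in fixed bins, for example four of 5 minutes:

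- fixed effects: bin, treatment, bin × treatment, group and the pre-window value;
- random effects: participant, and session within participant;
- residuals: serial correlation between bins of the same session.

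Prespecify one onset contrast in one named parameter, for example C = D(1) − D(4) as defined in the working, with D(1) and D(4) reported beside it. Treat the other parameters as exploratory, so that only one test addresses the hypothesis. The bin length and the parameter are for the trial team to choose, but before the data are seen. If the team does not want this model, the minimum is to label sub-hypothesis 3 exploratory with no planned test.

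**Cost.** Some text in two sections, slightly tighter session timing and modest extra analysis. No new device, visit or participant is needed.

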**6. Introduction****6.1 Background Information**

Stress is a well-established factor in the onset and persistence of burnout, anxiety, mood, and psychotic disorders. Sleep disorders further predispose individuals to, and exacerbate, these psychiatric symptoms. Individuals with mental health problems tend to have higher (social) stress reactivity and impaired stress recovery, which is compounded by sleep disturbances and sleep deprivation.

Relaxation can reduce stress, thereby potentially improving mental health symptoms. Moreover, stress-reducing interventions may enhance quality of life, social functioning, and occupational performance. While current stress-reducing interventions appear effective, they often require mental effort—such as focus and concentration—which may be compromised in patients.

To bridge this gap, a new e-Health application called **VRelax** has been developed. VRelax is a virtual reality self-management tool designed to reduce stress. It requires significantly less effort than traditional relaxation exercises due to its immersive qualities and has an immediate effect on perceived stress and emotional mental states.

Following a comprehensive literature review on the potential applications of Virtual Reality (VR) in forensic psychiatric populations—published in November 2021 in the *Tijdschrift voor Psychiatrie*—this study will be the first to assess the effects of VR-based relaxation in such a setting. The study aims to determine whether VR relaxation provides added value for both patients and staff, and how best to implement this technology within the hospital's operations.

Given that VR environments can simulate highly realistic situations that forensic psychiatric patients would otherwise be unable to experience due to their restricted freedoms, VR offers a powerful tool that addresses the limitations of confinement. The highly immersive nature of the application also benefits patients who are unable to engage in traditional relaxation exercises due to limited imagination or empathy skills.

This study will investigate the short- and medium-term effects of VRelax on both acute and chronic stress and compare these effects to a standard relaxation exercise of the participant's choice (Treatment As Usual, TAU). The study is based on previous work by Veling et al. (2021), in which the same VRelax application was tested in an outpatient setting.

---

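### The only test named for PSS is a pre-post paired t-test within a block, which cannot isolate a VR effect on chronic stress; specify a VR-versus-standard PSS model on the data already collected

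*Combined protocol and SAP*

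**What the plan says.** Section 6.1 sets the aim: to study the "short- and medium-term effects of VRelax on both acute and chronic stress and compare these effects to a standard relaxation exercise" chosen by the participant.

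The hypotheses are narrower. Hypothesis 3 reads "VRelax will also reduce chronic stress through a cumulative effect", and goes on: "meaning the post-intervention PSS score will be lower than the pre-intervention PSS score". It names no comparator. Hypothesis 2 is the VR-versus-standard claim, and it says that "VAS scores and biomarkers will reflect a stronger relaxation effect"; PSS is not mentioned.

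On data, section 13.1 provides for four PSS values per participant: "At the beginning and end of each 10-session block, general stress levels are measured using the Perceived Stress Scale (PSS"). Each participant has one VR block and one standard block.

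On analysis, section 16.2 states: "Perceived Stress Scale (PSS) scores will also be compared between pre- and post-therapy blocks (each block consisting of 10 sessions) using a paired t-test". Directly afterwards it introduces a mixed model, "To estimate the difference in effect between the VR treatment and standard relaxation", with time, treatment, group, the time-by-treatment interaction and a random intercept for participant. The outcome of that model is not named, and there is no term for block order (period). The carry-over check at the end of the section covers VAS scores and physiological parameters, not PSS.

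PSS is not listed as a primary or secondary endpoint in the synopsis or in section 8.

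**The concern.** A before-after test within the VR block asks whether PSS fell while patients were having VR sessions. It does not ask whether VR caused the fall. PSS may fall over ten sessions because time passes on the ward, because patients who enter at a stressful moment regress towards their mean, because they receive regular attention, or because any scheduled relaxation helps. The standard block exists to remove these explanations, and the named PSS test does not use it.

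At stake is the conclusion on hypothesis 3. Followed as written, the plan could declare that VRelax reduces chronic stress on evidence that does not come from the randomised comparison. Chronic stress is a numbered hypothesis, and section 7.1 asks about long-term impact, so readers will look for this result.

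**Working it through.** **Passages side by side.**

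| Place | What it covers | PSS named? | VR compared with standard? |
|---|---|---|---|
| 6.1 | Aim, acute and chronic stress | Chronic stress, not the scale | Yes |
| Hypothesis 2 | VAS, biomarkers | No | Yes |
| Hypothesis 3 | Chronic stress | Yes | No |
| 13.1 | Start and end of both blocks | Yes | Data allow it |
| 16.2, t-test | Before and after a block | Yes | No |
| 16.2, mixed model | Outcome not named | Unclear | Yes |
| 16.2, carry-over check | VAS, physiology | No | No |

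The comparison is announced and the data are collected, but no sentence assigns PSS to a comparative test.

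**The plan's own figure.** The documents give no PSS sample size, SD, effect or power. The stated 54 is for VAS relaxation. It reproduces with a two-sided paired t-test, difference 0.5 and zero correlation: SD of difference = √(0.83² + 0.74²) = 1.112, n = 41, and 41 × 1.3 = 53.3, rounded up to 54. It says nothing about PSS. I use it only for the number of completers: 54 × (1 − 0.30) = 37.8, taken as 38.

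**How often the VR-block t-test is significant when VR adds nothing.** Assumptions: PSS improves by the same amount d in both blocks, in units of the SD of block change; two-sided alpha 0.05 (the plan does not state sidedness). The test is a paired t-test with n − 1 degrees of freedom and noncentrality d√n. For n = 38 and d = 0.3, the noncentrality is 0.3 × √38 = 1.85 and the critical t is 2.026.

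| Shared change d | n = 38 | n = 54 |
|---|---|---|
| 0.3 SD | 0.44 | 0.58 |
| 0.4 SD | 0.67 | 0.82 |
| 0.5 SD | 0.85 | 0.95 |

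In a simulated two-sequence crossover (20,000 runs per scenario, 1:1 allocation, correlation of block changes 0.3, no carry-over), the VR-versus-standard contrast of changes stays at about 0.05 in every scenario. The data can therefore answer the question if the right contrast is specified.

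**What the comparison can detect.** For the contrast of block changes, the SD of the difference is √(2(1 − ρ)). With 80% power, the smallest detectable difference is 0.47 SD of block change (ρ = 0.5) to 0.66 SD (ρ = 0) with 38 completers, and 0.39 to 0.55 SD with 54.

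For a block-1-only comparison with 19 per group, the noncentrality is δ/√(2/19) on 36 degrees of freedom. Power of 80% needs δ of about 0.93 SD of PSS, unadjusted. If entry PSS correlates 0.5 with the outcome (assumed), this becomes 0.93 × √(1 − 0.25) = 0.81 SD.

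**Carry-over.** No washout or interval between blocks is stated, and hypothesis 3 expects a cumulative effect. In VR-first patients the second block is the standard block.
- If the VR effect persists, their end-of-block-2 PSS is lowered under standard relaxation, and an end-of-block contrast is pulled towards zero.
- If the effect fades during block 2, their PSS rises over the standard block, and a contrast of changes exaggerates VR.

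The first block is free of both problems.

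**The case against.** The strongest reply is that the mixed model may already cover PSS. It comes immediately after the PSS sentence, its purpose is the VR-versus-standard difference, and before/after coding suits a block as well as a session. This stands in part. A reader might infer that the plan excludes PSS from any comparison, but the text neither includes nor excludes it. What remains is that hypothesis 2 and the carry-over check list their outcomes without PSS, and that the model lacks a period term even if PSS is meant.

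Second, the t-test matches hypothesis 3, which is itself pre-post, and PSS is not a listed endpoint. Both facts are correct and limit the importance of the point. They do not help with interpretation: hypothesis 3 attributes the fall to VRelax, and section 6.1 announces a comparison.

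Third, a reader might infer that the team will treat a significant VR block beside a non-significant standard block as proof of a difference. The plan never proposes this. The chance of that pattern with no VR advantage also depends on the correlation between block changes. With 38 completers and a shared change of 0.3 or 0.4 SD it is about 22% to 25% if the two tests are independent, and about 12% to 20% at correlations of 0.3 to 0.7. I do not rest the point on it.

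Fourth, a carry-over argument against the VR-block t-test must be aimed correctly. A persisting VR effect in VR-first patients distorts their standard-block change, not their VR-block change.

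**Conclusion.** The point holds in this form: the only test named for PSS is an uncontrolled pre-post t-test. It cannot attribute a change in chronic stress to VR, and no analysis is clearly assigned to the comparison announced in section 6.1.

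It would be too strong to say that the trial cannot answer the question. The limitation lies in the named test, because the crossover design and the four PSS measurements can support a randomised contrast. Nor do the documents show that there is no washout, only that none is stated, and they do not say that sessions are one-to-one.

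The 44% to 85% range rests on assumed shared changes of 0.3 to 0.5 SD, 38 completers and two-sided testing. It illustrates the problem and does not predict what will happen. The change should be made, but it does not affect the primary endpoint.

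**What to change.** In section 16.2, make the main PSS analysis a mixed model on end-of-block PSS, with treatment, period and sequence as fixed effects, participant as random effect and study-entry PSS as covariate. Report the VR-minus-standard difference with a 95% CI.

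Add a comparison of the two randomised groups at the end of block 1 only, adjusted for entry PSS, as an estimate with a 95% CI. Carry-over cannot affect it. Keep the within-block t-tests as description, not as evidence of a VR effect. State which outcomes the existing time-by-treatment model covers.

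Write the limits into the plan: with no washout stated, persisting carry-over would pull the end-of-block contrast towards zero, and a null block-1 result would say little, given that only about 0.93 SD is detectable unadjusted.

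A lighter option is to name PSS as an outcome of the existing model and add a period term. That closes the ambiguity, but a contrast of changes stays exposed to a fading VR effect.

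The cost is SAP wording, one extra model and its block-1 check, all on data already collected. No new visits, measurements or participants are needed.
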